##### Conventional CT and MRI

This guideline has defined measurability of lesions on CT scan based on the assumption that CT slice thickness is 5 mm or less. If CT scans have slice thickness greater than 5 mm, the minimum size for a measurable lesion should be twice the slice thickness. MRI is also acceptable in certain situations (e.g. for body scans).

Use of MRI remains a complex issue. MRI has excellent contrast, spatial, and temporal resolution; however, there are many image acquisition variables involved in MRI which greatly impact image quality, lesion conspicuity, and measurement. Furthermore, the availability of MRI is variable globally. As with CT, if an MRI is performed, the technical specifications of the scanning sequences used should be optimized for the evaluation of the type and site of disease. Furthermore, as with CT, the modality used at follow-up must be the same as was used at baseline and the lesions should be measured/assessed on the same pulse sequence. It is beyond the scope of the RECIST guidelines to prescribe specific MRI pulse sequence parameters for all scanners, body parts, and diseases. Ideally, the same type of scanner should be used and the image acquisition protocol should be followed as closely as possible to prior scans. Body scans should be performed with breath-hold scanning techniques, if possible.

##### PET-CT

At present, the low dose or attenuation correction CT portion of a combined PET-CT is not always of optimal diagnostic CT quality for use with RECIST measurements. However, if the site can document that the CT performed as part of a PET-CT is of identical diagnostic quality to a diagnostic CT (slice thickness of 5

mm or less and generally with IV and sometimes with oral contrast), then the CT portion of the PET-CT can be used for RECIST measurements and can be used interchangeably with conventional CT in accurately measuring cancer lesions over time. Note, however, that the PET portion of the CT introduces additional data which may bias an investigator if it is not routinely or serially performed.

#### Ultrasound

Ultrasound is not useful in assessment of lesion size and should not be used as a method of measurement. Ultrasound examinations cannot be reproduced in their entirety for independent review at a later date and, because they are operator dependent, it cannot be guaranteed that the same technique and measurements will be taken from one assessment to the next. If new lesions are identified by ultrasound in the course of the study, confirmation by CT or MRI is advised. If there is concern about radiation exposure at CT, MRI may be used instead of CT in selected instances.

### 14.1.4 Response Criteria

#### *Evaluation of Target Lesions*

##### Complete Response (CR)

Disappearance of all target lesions. Any pathological lymph nodes (whether target or non-target) must have reduction in short axis to < 10 mm.

##### Partial Response (PR)

At least a 30% decrease in the sum of the diameters of target lesions, taking as reference the baseline sum diameters

##### Progressive Disease (PD)

At least a 20% increase in the sum of the diameters of target lesions, taking as reference the smallest sum on study (this includes the baseline sum if that is the smallest on study). In addition to the relative increase of 20%, the sum must also demonstrate an absolute increase of at least 5 mm. (NOTE: the appearance of one or more new lesions is also considered progression).

##### Stable Disease (SD)

Neither sufficient shrinkage to qualify for PR nor sufficient increase to qualify for PD, taking as reference the smallest sum diameters while on study. (Note: a change of 20% or more that does not increase the sum of the diameters by 5 mm or more is coded as stable disease).

To be assigned a status of stable disease, measurements must have met the stable disease criteria at least once after study entry at a minimum interval of 12 weeks ( $\pm 7$  days) after the date of Enrollment.

#### *Evaluation of Non-Target Lesions*

Complete Response (CR)

Disappearance of all non-target lesions. All lymph nodes must be non-pathological in size (<10 mm short axis)

Non-CR/Non-PD

Persistence of one or more non-target lesion(s).

Progressive Disease (PD)

Appearance of one or more new lesions and/or unequivocal progression of existing non-target lesions. Unequivocal progression should not normally trump target lesion status. It must be representative of overall disease status change, not a single lesion increase.

When the patient also has measurable disease, there must be an overall level of substantial worsening in non-target disease such that, even in the presence of SD or PR in target disease, the overall tumor burden has increased sufficiently to merit discontinuation of therapy. A modest “increase” in the size of one or more non-target lesions is usually not sufficient to qualify for unequivocal progression status. The designation of overall progression solely on the basis of change in non-target disease in the face of SD or PR of target disease will therefore be extremely rare.

When the patient only has non-measurable disease, the increase in overall disease burden should be comparable in magnitude to the increase that would be required to declare PD for measurable disease: i.e., an increase in tumor burden from “trace” to “large”, an increase in nodal disease from “localized” to “widespread”, or an increase sufficient to require a change in therapy.

Although a clear progression of “non-target” lesions only is exceptional, the opinion of the treating physician should prevail in such circumstances, and the progression status should be confirmed at a later time by the review panel (or Principal Investigator).

*Evaluation of New Lesions*

The appearance of new lesions constitutes Progressive Disease (PD).

A growing lymph node that did not meet the criteria for reporting as a measurable or non-measurable lymph node at baseline should only be reported as a new lesion (and therefore progressive disease) if it:

- a) increases in size to  $\geq 15$  mm in the short axis or;
- b) there is new pathological confirmation that it is disease (regardless of size).

*Evaluation of Best Overall Response*

The best overall response is the best response recorded from the start of the treatment until disease progression/recurrence or non-protocol therapy (taking as reference for progressive disease the smallest measurements recorded since the treatment started). The patient’s best response assignment will depend on the achievement of measurement criteria.

Target Lesions	Non-Target Lesions	New Lesions*	Best Overall Response	Remarks
CR	CR	No	CR	
CR	Non-CR/Non-PD***	No	PR	
CR	Not evaluated	No	PR	
PR	Non-PD***/not	No	PR	
SD	Non-PD***/not evaluated	No	SD	Documented at least once $\geq$ 12 wks. from study entry
PD	Any	Yes or No	PD	No prior SD, PR or CR
Any	PD**	Yes or No	PD***	
Any	Any	Yes	PD	

* See RECIST 1.1 manuscript for further details on what is evidence of a new lesion.  ** In exceptional circumstances, unequivocal progression in non-target lesions may be accepted as disease progression.  ***PD in non-target lesions should not normally trump target lesion status. It must be representative of overall disease status change, not a single lesion increase. Please refer to the Evaluation of Non-Target Lesions – Progressive Disease section for further explanation.  NOTE: Patients with a global deterioration of health status requiring discontinuation of treatment without objective evidence of disease progression at that time should be reported as “symptomatic deterioration.” Every effort should be made to document the objective progression even after discontinuation of treatment.
				

**Table 14. RECIST 1.1 For Patients with Measurable Disease (i.e. Target Disease)**

***Duration of Response***

Duration of Overall Response

The duration of *overall response* is measured from the time measurement criteria are met for CR or PR (whichever is first recorded) until the first date that recurrent or progressive disease is objectively documented (taking as reference for progressive disease the smallest measurements recorded since the treatment started).

The duration of *overall CR* is measured from the time measurement criteria are first met for CR until the first date that progressive disease is objectively documented.

#### Duration of Stable Disease

Stable disease is measured from the start of the treatment until the criteria for progression are met, taking as reference the smallest measurements recorded since the treatment started, including the baseline measurements.

To be assigned a status of stable disease, measurements must have met the stable disease criteria at least once after study entry at a minimum interval of 12 weeks (84 days,  $\pm 7$  days) after the date of Enrollment.

### **14.2 Progression-Free Survival (PFS)**

Patients will be evaluated during treatment and by follow-up assessments post-treatment at: 30-days (+5 days). PFS is defined as the time from treatment initiation until documented disease progression or death (by any cause, in the absence of progression). In progression-free patients, PFS will be censored at the last evaluable tumor assessment (RECIST v1.1).

### **14.3 Overall Survival (OS)**

OS is defined as the elapsed time from start of treatment to death or date of censoring. Patients alive or those lost to follow-up will be censored at the last date of contact (or last date known to be alive).

## **15.0 ADVERSE EVENTS**

The descriptions and grading scales found in the revised NCI Common Terminology Criteria for Adverse Events (CTCAE) version 4.03 will be utilized for adverse event reporting.

### **15.1 Purpose**

Adverse event data collection and reporting, which are required as part of every clinical trial, are done to ensure the safety of patients enrolled in the studies, as well as those who will enroll in future studies using similar agents. Adverse events are reported in a routine manner at scheduled times during a trial. Additionally, certain adverse events must be reported in an expedited manner for timelier monitoring of patient safety and care.

### **15.2 Adverse Event**

Adverse Event (AE): Can be any unfavorable and unintended sign (e.g., an abnormal laboratory finding), symptom, or disease temporally associated with the use of a drug, medical treatment, or procedure without judgment about causality. An adverse event can arise from any use and from any route of administration, formulation, or dose including an overdose. This includes any newly occurring event or a previous condition that has increased in severity or frequency since initiation of a drug, medical treatment, or procedure.

#### Abnormal Findings

In any clinical assessment, a value outside the normal or reference range (such as a clinical laboratory, vital sign, or ECG) will not be reported or assessed as an AE unless that value is considered to be of clinical significance by the investigator. A value of clinical significance is one that leads to discontinuation or delay in protocol treatment, dose modification, therapeutic intervention\*, or is considered to be a clinically significant new finding or change from baseline by the investigator.

\*Transfusion support administered to offset clinical symptoms of anemia or thrombocytopenia will not be considered therapeutic intervention.

#### Signs and Symptoms

Signs/symptoms resulting from an underlying clinical diagnosis should be documented as one comprehensive AE. If no underlying clinical diagnosis can be identified, each sign/symptom should be reported as a separate independent event. (A new or worsening event resulting from an underlying clinical diagnosis or a reaction to concurrent medications should be documented as a separate independent AE unless it is within the normal range of fluctuation for that patient.)

#### Grade Changes/Fluctuations

AEs will be reported at the maximum grade/severity experienced for the duration of the event. Should one particular event warrant further investigation, additional details may be collected at the discretion of the Principal Investigator.

#### Progression of Disease

Progression of disease, if documented in accordance to standard of care, should not be reported as an AE.

#### Tests and Procedures

Tests and procedures should not be reported as AEs. The underlying clinical diagnosis (or sign/symptom in the event an underlying clinical diagnosis is not known) requiring testing or a procedure, should be reported as an adverse event if it meets criteria for reporting.

### 15.3 Serious Adverse Events (see also Appendix A)

Serious AE (SAE) means any untoward medical occurrence that occurs at any dose:

1. Results in death.
2. Is life-threatening.

The term "life-threatening" in the definition of "serious" refers to an event in which the patient was at risk of death at the time of the event; it does not refer to an event which hypothetically might have caused death if it were more severe).

3. Requires inpatient hospitalization or prolongation of present hospitalization.

Elective hospitalization to simplify protocol treatment/evaluations or to treat a baseline condition that did not worsen from baseline will not be considered an SAE.

4. Results in persistent or significant disability/incapacity.  
Disability is defined as a substantial disruption of a person's ability to conduct normal life functions.
5. Is a congenital anomaly/birth defect.
6. Is a medically important event.  
A medically important event may not be immediately life threatening or result in death or hospitalization but may jeopardize the patient or may require intervention to prevent one of the other outcomes listed in the definition above, or involves suspected transmission via a medicinal product of an infectious agent. Examples of such medical events include allergic bronchospasm requiring intensive treatment in an emergency room or at home, blood dyscrasias or convulsions that do not result in inpatient hospitalization, or the development of drug dependency or drug abuse; any organism, virus, or infectious particle (e.g., prion protein transmitting Transmissible Spongiform Encephalopathy), pathogenic or nonpathogenic, is considered an infectious agent.

**Additional SAE classification(s) for AEs occurring at any dose or during any use of Merck product(s):**

6. Is a new cancer (that is not a condition of the study);
7. Is associated with an overdose (whether accidental or intentional): Any adverse event associated with an overdose is considered a serious adverse event. An overdose that is not associated with an adverse event is considered a non-serious event of clinical interest and must be reported within 24 hours.
8. Is another important medical event

Clarification should be made between the terms *serious* and *severe* because they ARE NOT synonymous. The term *severe* is often used to describe the intensity (severity) of a specific event (as in mild, moderate, or severe myocardial infarction); the event itself, however, may be of relatively minor medical significance (such as a severe headache). This is NOT the same as *serious*, which is based on patient/event outcome or action criteria described above and is usually associated with events that pose a threat to a patient's life or functioning. A severe AE does not necessarily need to be considered serious. For example, persistent nausea of several hours duration may be considered severe nausea but not an SAE. On the other hand, a stroke resulting in only a minor degree of disability may be considered mild but would be defined as an SAE based on the above noted criteria. Seriousness (not severity) serves as a guide for defining regulatory reporting obligations.

#### 15.4 Adverse Event Collection Period

In this protocol, adverse events include only treatment-emergent adverse events. A treatment-emergent adverse event (TEAE) is defined as any event that begins or worsens after the start of protocol treatment. All baseline-emergent adverse events, any event that begins or worsens after completion of the informed consent protocol but prior to the start of protocol treatment, should be reported as a Baseline/Comorbid Condition.

All adverse events that occur within  $\leq 30$  days of the last dose of study therapy will be reported and followed until resolution. Resolution is defined as a return to baseline status or the stabilization of an event with the expectation that it will remain chronic. (Exception: If a patient begins an alternative therapy that confounds accurate assessment of AEs within  $\leq 30$  days of the last dose of study therapy, all adverse event collection will stop and any ongoing events will be left open.)

#### 15.5 Adverse Event Reporting Requirements

The information to be reported in AEs will be assessed by and assigned severity using the National Cancer Institute Common Terminology Criteria for Adverse Events (NCI CTCAE), Version 4.03. The NCI CTCAE provides descriptive terminology and a grading scale for each adverse event listed. A copy of the NCI CTCAE v4.03 can be downloaded from the CTEP home page (<http://evs.nci.nih.gov/ftp1/CTCAE/About.html>).

Information to be reported in the description of each adverse event may be included, but is not limited to:

1. Clinical Diagnosis of the event as determined by NCI CTCAE, Version 4.03 descriptive terminology. If no clinical diagnosis can be identified, each sign/symptom should be reported as a separate independent event.
2. Date of onset of the AE (start date).
3. Date of resolution of the AE (end date).
4. Severity of the event determined by NCI CTCAE, Version 4.03 grading scale.
5. Relationship of the AE to study therapy. Categorized as follows:

Definite	The adverse event is clearly related to the investigational agent(s)
Probable	The adverse event is likely related to the investigational agent(s)
Possible	The adverse event may be related to the investigational agent(s)
Unlikely	The adverse event is doubtfully related to the investigational agent(s)
Unrelated	The adverse event is clearly not related to the investigational agent(s)

6. Whether or not the AE is Serious or Not Serious as defined in Section 15.3 Serious Adverse Events.

7. Whether the AE is Suspected and/or Unexpected.

Suspected	Any AE for which there is a reasonable possibility that the drug caused the AE. For the purposes of expedited safety reporting, ‘reasonable possibility’ means there is evidence to suggest a causal relationship between the drug and the AE.
Unexpected	Any AE for which the nature or severity of the event is not consistent with the applicable product information, e.g., the Investigator’s Brochure or Package Insert.

8. Action taken as a result of the AE.

9. Outcome.

### 15.6 Expedited Adverse Event Reporting Requirements

All AEs, regardless if serious or not, will be described in the source documents, reported on the applicable AE page of the CRFs, and entered into *Velos*. However, certain adverse events must also be reported in an expedited manner for more timely monitoring of patient safety and care. Appendix A provides information about these expedited reporting requirements.

## 16.0 STATISTICAL CONSIDERATIONS

### 16.1 Overview

This single-arm phase II study will assess the progression-free rate at 3 months after concurrent axitinib and pembrolizumab therapy in advanced soft tissue sarcomas not amenable to traditional chemotherapy or that have failed standard of care treatment. (See Section 7.0, Study Design). Sample size justification of 30 patients is provided in Section 16.4 based on single-arm survival design.

### 16.2 Definitions and Endpoints

#### Analysis set

Analysis set: The analysis set for evaluation of treatment response consists of all study-eligible patients who receive at least 80% of scheduled axitinib doses and two infusions of pembrolizumab, have measurable disease at baseline and at least one post-baseline disease assessment. The analysis set for the second endpoint of toxicity will include all study-eligible patients who receive at least one dose of both drugs.

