### 3.2 Secondary endpoints

- The objective response (CR/PR), clinical benefit (CR/PR/SD), time to progression (TTP), and overall survival (OS) defined as time from study treatment initiation to first occurrence of progression by RECIST v1.1 or death of sarcoma patients treated with concurrent axitinib/pembrolizumab therapy.

Evaluable criteria:

Eligible subjects enrolled into the study that received at least 80% of scheduled axitinib doses and two infusions of pembrolizumab, have measurable disease at baseline and at least one post-baseline disease assessment.

- Adverse events, including dose-limiting toxicity and serious adverse events (grade 3 or 4) will be graded using NCI CTCAE version 4.03.

Evaluable criteria:

Eligible subjects enrolled into the study that receive at least one dose of both axitinib and pembrolizumab. Patients who withdraw from the study prior to week 2 for any reason other than DLT or other significant toxicity will not be considered evaluable for toxicity.

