### 7.2 Dose-Limiting Toxicity (DLT)

Dose-Limiting Toxicity (DLT) is defined as any one of the following Adverse Events (AEs) that occurs during the first cycle (49 days) and is considered by the Investigator to be related (possible, probable, or definite) to study drug, specifying attribution to axitinib, pembrolizumab, or both. Management and dose modifications associated with the above AEs are outlined in Section 10.0 (Treatment/Dose Modifications).

DLT is defined as any one of the following (Table 4 and 5):

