**Table 4. Summary of Lab DLTs.**

**Non-Lab Toxicity**

AE	Patient Population	Dose Limiting Toxicity
Rash (acneiform or macro-papular)	All	≥ Grade 3
Palmar-plantar erythrodysethesia syndrome	All	Grade 3
Hypertension	Uncontrollable to less than 150/90 with maximal medical management within 7 days	≥ Grade 3
Bronchopulmonary hemorrhage (hemoptysis)	All	≥ Grade 3
Mucositis oral (Stomatitis)	Non-responsive to maximal supportive medication within 7 days	≥ Grade 3
Other Non-Lab Toxicity	All	≥ Grade 3 with the EXCEPTION of the following: 
 
• nausea, vomiting, diarrhea, constipation or edema controllable with medication within 7 days
 
• grade 3 fever in the absence of infection or neutropenia
 
• tumor flare defined as local pain, irritation or rash localized at sites of known or suspected tumor
 
• transient grade 3 infusion reaction
 
• grade 3 thromboembolic event IF patient is asymptomatic and initiated on anticoagulation – as there is a high prevalence in sarcomas, and this is difficult to attribute to study drug.
 

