**Table 5. Summary of Non-Lab DLTs.**

### 8.0 TREATMENT PLAN

A cycle of treatment will consist of concurrent axitinib and pembrolizumab therapy for 6 weeks (Figure 3, Table 6), except for cycle 1 which will be 7 weeks as detailed above. Administration of axitinib shall occur continuously with pembrolizumab administered on day 8 and day 29 of the first cycle, and days 1 and 22 of the following cycles. The first five patients will not be dose-escalated above 5 mg PO twice daily axitinib. If these patients exhibit acceptable rates of DLT, starting with patient 6, dose-escalation of axitinib will be permitted. No dose escalations will be permitted during cycle 1. On day 1 of cycle 2 and the subsequent cycles, dose escalation of axitinib is permitted if toxicity is within the specified criteria. No dose-escalation will be conducted in the middle of any cycle. Dose reduction or interruption is permitted in the case of toxicity at any time as per section 10.0.

Trial treatment should be administered after all procedures/assessments have been completed as detailed in Section 12.0. Trial treatment may be administered up to 3 days before or after the scheduled Day 1 of each cycle due to administrative (e.g. scheduling) reasons.

Cycle(s)	1							2						Imaging prior to every subsequent odd cycle (i.e. 3, 5, 7, 9, etc.)	3, 4, 5, etc. until progression					
	1	2	3	4	5	6	7	1	2	3	4	5	6		1	2	3	4	5	6
Week(s)	1	8	1	2	2	3	4	1	8	1	2	2	36	1	8	1	2	2	3	
Day(s)	1	8	5	2	9	6	3	1	8	5	2	9	36	1	8	5	2	9	6	
Axitinib oral, BID continuously (uptitration permitted starting from cycle 2)	X	X	X	X	X	X	X	X	X	X	X	X	X	X	X	X	X	X	X	
Pembrolizumab IV q21 days		X			X			X			X			X			X			

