## 10.0 TREATMENT/ DOSE MODIFICATIONS

### 10.1 Unacceptable Toxicity

Causality for all adverse events should be assessed and if deemed attributable, attempts should be made to attribute to either axitinib, pembrolizumab, or potentially both agents.

In the case of toxicities refractory to routine medical management which are assessed as possibly attributable to both drugs (i.e. liver enzyme elevation, renal dysfunction, thyroid dysfunction, diarrhea/colitis) that may be autoimmune in origin, dose interruption of axitinib should be attempted first. Generally prompt resolution of the toxicity is observed if attributable to axitinib. If the toxicity is persistent, treatment should be administered as per the pembrolizumab treatment guidelines below, including corticosteroid therapy where advised.

Drug-related grade 4 toxicities will generally require subject to discontinue all study treatment. Exceptions include the following: 1) clear evidence that the toxicity was attributable to axitinib alone, resolved upon cessation of axitinib, and there is rationale to continuing pembrolizumab monotherapy 2) Grade 4 lab abnormalities that are not immune-related, where the patient is asymptomatic, and the abnormalities can be reversed with medical treatment. Example: grade 4 hypertriglyceridemia that responds to antilipid drugs. Intolerable grade 2 and grade 3 toxicities should be managed as per dose modification guidelines listed in the tables below. For grade 2 and grade 3 toxicities attributable to axitinib that do not resolve to  $\leq$  grade 1 within 3 weeks of holding study drug, axitinib should be permanently discontinued. Pembrolizumab therapy may be continued providing the residual adverse events are within permissible ranges for pembrolizumab dosing.

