##### Evaluable for Toxicity

All eligible patients who receive at least 80% of scheduled doses of axitinib during weeks 1-4, and receive pembrolizumab during week 2. Patients who withdraw from the study prior to week 2 for any reason other than DLT or other significant toxicity will not be considered evaluable for toxicity

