#### Exclusions

Patients who are enrolled on study but do not complete the first cycle and drop out due to any reason except dose limiting toxicity (DLT) or clinical progression will be excluded from analysis of efficacy endpoints. Reasons for such exclusions will be characterized such as consent withdrawn or eligibility subsequently not confirmed.

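### The protocol defines the toxicity population in three conflicting ways; read literally, two of them can leave patients out because of the toxicity being measured

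*Combined protocol and SAP*

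**What the plan says.** Three sections say who counts for toxicity.

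| Section | Base rule | Clause on leaving before week 2 |
|---|---|---|
| 16.2, Analysis set | One dose of each drug | None |
| 3.2, Secondary endpoints | One dose of each drug | Not evaluable, unless the reason was DLT or significant toxicity (implied) |
| 14.1.1, Evaluable for Toxicity | 80% of axitinib in weeks 1-4, and pembrolizumab in week 2 | As in 3.2 (implied) |

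The text of 16.2 is: "The analysis set for the second endpoint of toxicity will include all study-eligible patients who receive at least one dose of both drugs". In 3.2, patients who leave "prior to week 2 for any reason other than DLT or other significant toxicity will not be considered evaluable for toxicity". In 14.1.1 the same sentence opens "Patients who withdraw from the study prior to week 2 for any reason other than DLT or other significant toxicity".

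Other relevant text:
- Section 8.0 has "pembrolizumab administered on day 8 and day 29 of the first cycle", so axitinib is given alone on days 1-7.
- Section 7.2 counts DLTs over the first cycle of 49 days, which includes that week.
- Section 10.1: "Drug-related grade 4 toxicities will generally require subject to discontinue all study treatment". It then allows exceptions, one of them for toxicity due to axitinib alone.
- Section 16.3 reports the number of patients treated and the numbers with DLT, SAEs and grade 3 or higher events.
- Section 17.0 applies its lead-in stopping rule to the first five treated patients.

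**The concern.** A safety population should not depend on whether the patient tolerated the treatment. Under 16.2, a patient reaches the set only by surviving the axitinib week well enough to receive pembrolizumab. A patient stopped by axitinib toxicity before day 8 leaves both numerator and denominator, and leaves because of the event being counted. The base rule in 14.1.1 has the same property over a longer window, because holding axitinib for toxicity is what brings a patient below 80%.

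Describing safety is a secondary objective (2.2). The final table could show fewer DLTs than the monitoring committee saw. In the extreme case, a treatment-related death in days 1-7 would suspend enrolment under 17.0 yet fall outside the 16.2 set. With three definitions in one document, the analyst would also have to choose a denominator after the data are in.

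**Working it through.** **1. The plan's own toxicity figures.** Section 7.1 expects a 30% DLT rate; section 1.3 reports 3 DLTs in 10 evaluable patients, and 3/10 = 30%. Section 17.0 uses a Beta(0.6, 1.4) prior and suggests stopping when P(rate > 40%) is at least 90%. The prior probability above 40% computes to 0.320 (stated 32%). The posterior after x DLTs in n patients is Beta(0.6 + x, 1.4 + n − x); for 4 of 5 it gives 0.920, so the 4-of-5 boundary reproduces.

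**2. Who is lost under 16.2.** Seven of the 49 DLT days precede the second drug. A patient is lost only if all treatment ends in those seven days. Section 10.1 provides the route through grade 4 toxicity. The group is narrow for two reasons:
- Section 10.1 can let pembrolizumab go ahead after toxicity due to axitinib alone, and one pembrolizumab dose puts the patient in the set.
- Hypertension, mucositis, kidney injury and proteinuria become DLTs only if uncontrolled or unresolved over 7 days, so they can mostly not be confirmed before day 8. Other non-laboratory events, "≥ Grade 3 with the EXCEPTION of the following" a short list, count at once.

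**3. Who is lost under 14.1.1.** Weeks 1-4 hold 28 × 2 = 56 axitinib doses, and 0.80 × 56 = 44.8, so 45 are needed. This assumes that held doses still count as scheduled, which the text does not settle.

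| Days held | Doses taken | Share | Meets 80%? |
|---|---|---|---|
| 3 | 50/56 | 89.3% | Yes |
| 5 | 46/56 | 82.1% | Yes |
| 6 | 44/56 | 78.6% | No |
| 21 | 14/56 | 25.0% | No |

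The 3-5 day hold in 10.2 passes. A hold of six days or more fails, although 10.1 allows up to 3 weeks for grade 2-3 axitinib toxicity to resolve. The implied exception covers only withdrawal before week 2, so it does not rescue these patients. The documents give no frequency for such holds.

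**4. Size under 16.2.** Let N be treated patients, x those with a DLT, and k those with a DLT who never receive pembrolizumab. The full rate is x/N and the literal 16.2 rate is (x − k)/(N − k), which is lower whenever k > 0 and x < N. At 30%, x = 12 for N = 40 and x = 9 for N = 30.

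| k (assumed) | N = 40 | N = 30 |
|---|---|---|
| 0 | 12/40 = 30.0% | 9/30 = 30.0% |
| 1 | 11/39 = 28.2% | 8/29 = 27.6% |
| 2 | 10/38 = 26.3% | 7/28 = 25.0% |
| 3 | 9/37 = 24.3% | 6/27 = 22.2% |

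Exact (Clopper-Pearson) 95% intervals are 16.6-46.5% for 12/40 and 15.0-44.9% for 11/39. The shift is 30.0 − 28.2 = 1.8 points. If the lost patient is the only case of a rare serious event, 1/40 = 2.5% (0.1-13.2%) becomes 0/39 = 0% (0-9.0%).

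**The case against.** The strongest reply is that the loss is not settled. The pre-week-2 clauses in 3.2 and 14.1.1 have an effect only if patients stopped early by toxicity stay evaluable, and 16.3 speaks of patients treated. This stands, and it is why the finding is a conflict between sections and not a fixed exclusion. It does not remove the problem. The exception is only implied, it follows base rules that themselves require pembrolizumab, and 16.2, where the analysis set is defined, omits it.

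A both-drugs population is also defensible, because the objective in 2.2 concerns the combination. That supports keeping such a table, but not making it the only one. No events go unrecorded: 15.6 puts all AEs on the CRF, and 16.3 reports discontinuations with reasons. Only membership of the rates is at issue.

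A reader might infer three stronger things that the documents do not support:
- **That the stopping rule is weakened.** If the 16.2 set governed the lead-in, 4/5 (posterior 0.920, stop) would become 3/4 (0.842, continue). But 17.0 counts treated patients and runs its toxicity period from the start of treatment.
- **That every week-1 axitinib toxicity is lost.** Section 10.1 often lets pembrolizumab proceed.
- **That the Exclusions paragraph of 16.2 removes patients from toxicity.** It concerns those who "drop out due to any reason except dose limiting toxicity (DLT) or clinical progression will be excluded from analysis of efficacy endpoints". It shows that a DLT exception was written for efficacy, and nothing about toxicity.

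**Conclusion.** The point holds as an inconsistency with a predictable direction. Sections 16.2, 3.2 and 14.1.1 name three toxicity populations. Read literally, 16.2 omits patients whose treatment ends for axitinib toxicity in days 1-7, and 14.1.1 could also omit patients whose axitinib is held for toxicity in weeks 1-4.

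The 16.2 effect is small. With 0 or 1 of 40 patients affected (an assumption; no week-1 rate is given), a 30% DLT rate falls by at most 1.8 points, well inside its interval. It matters most for a single rare serious event, which would vanish from the rate. The 14.1.1 effect could be wider but cannot be sized from the documents. Its direction is a tendency only: dropping a patient whose toxicity was not a DLT lowers the rate of that toxicity but slightly raises the DLT rate.

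No stated design figure changes. Confidence is high on the wording and low on how many patients it would touch.

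**What to change.** Use one definition in 16.2, 3.2 and 14.1.1: the safety set is all patients who receive any dose of either study drug. Flag axitinib-only events from days 1-7 in the main table. Keep the both-drugs set as a supplementary table for combination toxicity.

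At minimum, write the exception for DLT or significant toxicity explicitly into 16.2, and remove the 80% dose condition in 14.1.1 for patients with toxicity.

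The cost is wording in three sections. Section 20.5 already requires a CRF for every patient given any study treatment, so no new data are needed. The downside is that the main table will include a few patients who took only axitinib, among them early leavers without toxicity who enlarge the denominator. The supplementary table answers that.
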